11. METHODOLOGY

The registry is designed to document the disease progression in patients with advanced renal cell carcinoma, relapsed/refractory mantle cell lymphoma, and gastrointestinal stromal tumor intended by the treating physician for systemic therapy.

During the course of the registry, the following (minimum) number of survey times and endpoints are planned:

At observation start: Enrollment Visit

During the course of the observation: Follow-up documentation (as per local guidelines, generally every

8 - 12 weeks)

End of observation: Completion/Discontinuation Form

1-year follow-up for subjects who discontinue therapy: Survival form (every 6 months thereafter)

[figure not shown]
The temporal sequence and number of follow-up documentation items depends on medical practice to perform confirmatory imaging procedures and patient survival.

The completion of the continuous observation documentation (follow-up visits) takes place with the completion or discontinuation of the case report form below:

- Patient death.
- Patient lost to follow up due to patient request/withdrawal of patient informed consent,
- Change in therapy or discontinuation due to intolerance to temsirolimus, sunitinib, and axitinib or progression.

For the indication **metastatic renal cell carcinoma**, prospective documentation of sequential therapy is an option. According to the approvals of temsirolimus, sunitinib and axitinib, e.g. the following therapy sequences are possible:

• Sunitinib (as first-line therapy) followed by axitinib

- Temsirolimus (as first-line therapy) followed by sunitinib
- Axitinib (as second-line therapy, 1st Pfizer therapy sequence) followed by sunitinib
- Sunitinib (as first-line therapy) followed by a second-line approved active substance (interim documentation) followed by axitinib (in the third line or a later line)

Herein two consecutive Pfizer lines of therapy or two Pfizer lines of therapy with one or more intermediate therapies can be documented. The following documentation sheets are available for this purpose:

White documentation section: 1. Pfizer Therapy sequenze, e.g. Sunitinib

- Enrollment Visit
- Follow-up documentation every 8-12 weeks
- Final Assessment/Discontinuation of documentation

Pink Documentation section. Interim documentation for non-Pfizer products, e.g. nivolumab

• Every 8-12 weeks

Green documentation section. 1. Pfizer Therapy Sequence

- Initial visit to change treatment
- Follow-up documentation every 8-12 weeks

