In total, the treatment of approximately 100 patients per year and product should be documented. This number of patients was chosen to capture a broad range of medical prescription habits and assess the target criteria as significantly as possible. The probability of occurrence of at least one "uncommon" (>1/1000, <1/100) AE is between 0.33 and 0.98 and for a "rare" AE (>1/10,000,<1/1000), between 0.04 and 0.33.

The planned number of 200 sites to be included according to Amendment III allows a representative cross-section across German oncology practices or clinics.

With Amendment VI, the efficacy of axitinib regarding the progression-free survival and overall survival is to be evaluated in the 3rd (and 4th) line of therapy and a correlation with patients on axitinib in the 2nd line of therapy is to be performed.

Patients already documented in STAR-TOR (n = 92; status of 06/30/2017) who received axitinib in the 2nd line of therapy, i.e. with a treatment course of sunitinib-axitinib, will be used as a (historical) comparison group for the comparison with the 3rd and 4th line of therapy, particularly because patients with axitinib in the 2nd therapy line are only rarely expected after the guideline amendments and therefore cannot be newly enrolled.

Patients already documented in STAR-TOR with axitinib in the 3rd line of therapy or 4th line of therapy should not be used to answer the expanded question (see above) as none of these patients received nivolumab or another active substance newly approved in 2016 in the 2nd line of therapy, but received other therapeutic options. It cannot be excluded that the deviating pretreatment/treatment course will impact the efficacy of axitinib in the subsequent lines of therapy as compared with current therapy guidelines.

[figure not shown]
Approximately 45 patients with a PFS event should be documented in the 3rd line with axitinib after the previous therapy sequence, e.g. sunitinib - nivolumab. Therefore, mPFS and mOS can be estimated with sufficient precision (see Statistical Analysis Plan). In order to recruit 45 new third-line axitinib patients after e.g. sunitinib-nivolumab pretreatment in STAR-TOR, approximately 45 months will be required (assuming the usual therapy periods).

Assuming that the last patient is enrolled after 45 months and a progression event (or death) occurs after approximately 6 months, a runtime of approximately 4 years should be assumed after implementation of Amendment VI.

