5 ANALYSIS SETS/POPULATIONS

Analyses will be performed within each indication and treatment, e.g. one for mRCC and temsirolimus, sunitinib and axitinib, one for the non-Pfizer interim therapies and one for MCL and one for GIST.

For data from mRCC patients included prior to amendment VI of the protocol baseline data from sequence 1 will be forwarded as baseline data for sequence 2, if the respective data is not asked for in follow-up 1 of sequence 2 (tumor anamnesis at time of primary diagnosis, prior local and systemic therapies, prior and concomitant diseases, concomitant medication (other than systemic therapy)). Ongoing adverse events from sequence 1 have to be added to the list of concomitant diseases in sequence 2. Additional cancer therapy from baseline and follow-up visits of sequence 1 will be forwarded as baseline data for sequence 2 unless the therapy has been discontinued.

For patients included under amendment VI, baseline data for the second Pfizer treatment will be asked for in the CRF as changes in this data are not completely asked for in the non-Pfizer treatment periods.

For data from mRCC patients the following tables (see chapter 9): demographic information (1.2-1; 1.2-2), study periods (1.1-5.2), previous local and systemic therapy (1.5-1; 1.5-2), duration of therapy (1.6-1), overall survival (2.2-1), progression free survival (2.3-1), course of Karnofsky performance scale (2.5) and course of FKSI-15 (2.6), EQ-5D (2.7) will be repeated for the following groups of patients:

- Treatment sequence 1^{st} sunitinib $\rightarrow 2^{nd}$ axitinib \rightarrow any further therapy
- Treatment sequence 1^{st} temsirolimus $\rightarrow 2^{nd}$ sunitinib \rightarrow any further therapy
- Treatment sequence 1^{st} sunitinib \rightarrow any further therapy (no axitinib in 2^{nd} line)
- Treatment sequence 1^{st} temsirolimus \rightarrow any further therapy
- Treatment sequence 1^{st} sunitinib \rightarrow no further therapy
- Treatment sequence 1^{st} temsirolimus \rightarrow no further therapy
- Any therapy $\rightarrow 2^{\text{nd}}$ axitinib \rightarrow any further therapy.

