1.3-1.4	Tumor anamnesis - other information	GIST	SAFETY, EAS	.1 Frequency table for size of primary tumor, sample statistics for number of mitoses, frequency table for primary mutation analysis performed?, frequency table for type of KIT-mutation .2 Frequency table for mutation analysis performed in recidive?, frequency table for type of mutation
CCI				
1.3-3	ECG	mRCC, GIST	SAFETY, EAS	Frequency tables for normal/abnormal ECG by time window

Table No.	Title	Treatment/ Indication	Analysis set	Description
CCI				

Table No.	Title	Treatment/ Indication	Analysis set	Description
CCI				
				, number of transplantations, R0 resection reached

Table No.	Title	Treatment/ Indication	Analysis set	Description
CCI				

Table No.	Title	Treatment/ Indication	Analysis set	Description
CCI				
2	Effectiveness			
2.1	Response to therapy			
2.1-1	Course of response to therapy	All	EAS	Frequency table by time window (in total and by patient risk groups)

Table No.	Title	Treatment/ Indication	Analysis set	Description
2.1-2	Best response	All	EAS	Frequency table for best response in total and confirmed / not-confirmed (the latter not for Torisel® MCL); Frequency table for best response excluding patients "not assessable" only for MCL Listing of reasons for not assessable best response; Frequency table for best response by patient risk groups
2.1-3	Used diagnosis technique	All	EAS	CT, Thorax X-ray, MRT, Ultrasonic testing, PET, Bone scan, Clinical (by time window and for best response)
2.2	Overall survival			
2.2-1	Kaplan-Meier estimates for Overall survival	All	EAS Sequence analysis	Time to 25%, median and 75% survival with confidence intervals incl Kaplan-Meier curve on all patients
2.2-2	Kaplan-Meier estimates for Overall survival by patient risk groups	mRCC	EAS	 .1 Physicians prognosis of patients risk .2 Risk groups according to Motzer score .3 Risk groups according to modified Motzer score .4 Risk groups according to Motzer score for pretreated patients .5 by treatment sequence .6 by treatment and treatment line. .7 1st line patients by risk (poor vs. non-poor) .8 by LDH ≤ 300 U/l vs > 300 U/l incl. Log-ranktest and Kaplan-Meier curves

Table No.	Title	Treatment/ Indication	Analysis set	Description

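### As worded, the SAP's mRCC sequence groups leave out patients who stop after second-line axitinib, so overall survival in the sunitinib-axitinib group is conditioned on starting a third therapy

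*SAP*

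**What the plan says.** SAP section 5 names a set of mRCC tables that "will be repeated for the following groups of patients". The set is study periods (1.1-5.2), demography (1.2-1, 1.2-2), previous therapy (1.5-1, 1.5-2), duration of therapy (1.6-1), overall survival (2.2-1), PFS (2.3-1), Karnofsky status (2.5), FKSI-15 (2.6) and EQ-5D (2.7). Seven groups follow, numbered here in the SAP's order:

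1. sunitinib first, axitinib second, then a further therapy
2. temsirolimus first, sunitinib second, then a further therapy
3. sunitinib first, then "any further therapy (no axitinib in 2^{nd} line")
4. temsirolimus first, then a further therapy
5. sunitinib first, then "no further therapy"
6. temsirolimus first, then "no further therapy"
7. any first therapy, axitinib second, then a further therapy

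Groups 1 and 7 both end in the string "axitinib \rightarrow any further therapy". The SAP does not define the phrase.

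The protocol attaches no third therapy to the same course. Section 11 lists "Sunitinib (as first-line therapy) followed by axitinib" as a possible sequence, and its case number estimate counts 92 patients (status 06/30/2017) "who received axitinib in the 2nd line of therapy, i.e. with a treatment course of sunitinib-axitinib".

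**The concern.** The list uses the two endings as opposites: groups 3 and 5, and groups 4 and 6, differ in whether anything follows. On that usage the third position of groups 1, 2 and 7 requires at least one later therapy. Whether a patient gets one is known only after second-line treatment has ended, and patients who die on axitinib or soon after it can never qualify.

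SAP Appendix A1.3 counts overall survival from the baseline visit. Time survived up to the third therapy therefore counts as follow-up in a group that a patient can enter only by surviving it. This is immortal-time selection. It would affect the one set of tables that shows survival, performance status and quality of life for the sunitinib-axitinib course as such. The sequence of systemic therapies is a stated objective in protocol section 6 and SAP section 2.2.

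**Working it through.** The plan gives no figure to reproduce here: it is descriptive, with no hypotheses. The check has two parts.

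**Group membership.** Write S = sunitinib, T = temsirolimus, A = axitinib, O = other. All sequences of one to three lines starting with S or T were tested against the seven definitions, together with O-A. The test was run under two readings of the third position in groups 1, 2 and 7.

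| Sequence | At least one later therapy | Later therapy optional |
|---|---|---|
| S | 5 | 5 |
| S-O | 3 | 3 |
| S-A | none | 1, 7 |
| S-A-O | 1, 7 | 1, 7 |
| T-S | 4 | 2, 4 |
| T-A | 4 | 4, 7 |
| O-A | none | 7 |

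Under the literal reading, S-A is the only uncovered sequence among those starting with sunitinib or temsirolimus. O-A is also uncovered, although protocol section 7.2(c) enrols axitinib patients after a cytokine. T-S leaves its two-drug group but stays in group 4. Under the optional reading nothing in the table is uncovered, and groups 1, 3 and 5 divide first-line sunitinib patients without gap or overlap.

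**Size of the effect on overall survival (illustration only).** From the documents: n = 92, and 6 months for axitinib. The protocol gives the 6 months as an average observation period; it is used here as a median. Everything else is assumed. Times are exponential and run from the start of axitinib.

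*Setting A.* PFS has a median of 6 months, 15% of PFS events are deaths, and a share p of progressors starts a third therapy.

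- Patients kept = 92 × 0.85 × p. For p = 0.4, 0.5 and 0.6 this gives 31.3, 39.1 and 46.9.
- With median post-progression survival of 10 months after a third therapy and 4 months without one, median OS in all patients is 12.9, 13.5 and 14.1 months. In the kept patients it is 19.1 each time. The gap is 5.0 to 6.2 months.
- With 7 months for both, so that the third therapy carries no prognostic information, the medians are about 14.2 and 15.7. The gap is 1.5 months.

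*Setting B.* Death (median m, rate λ = ln2/m) and end of axitinib (median 6, rate μ = ln2/6) are independent, and third-therapy starters are a random subset of those alive when axitinib ends.

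- Among starters, P(OS > t) = [(λ+μ)e^(−λt) − λe^(−(λ+μ)t)]/μ.
- Setting this to 0.5 gives medians of 18.3, 25.1 and 31.5 months for m = 12, 18 and 24. The gaps are 6.3, 7.1 and 7.5 months.
- If 30%, 50% or 70% start a third therapy, 92 × share gives about 28, 46 or 64 patients. The 70% case is impossible for m = 12, because only μ/(λ+μ) = 67% outlive axitinib.

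The upward direction appears in every setting. The amount depends on the inputs.

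**The case against.** The strongest reply is that the trailing phrase was meant as a wildcard: whatever follows, if anything. The parenthesis in group 3 is needed only to separate it from group 1, which suggests that group 1 was meant to hold every sunitinib-axitinib patient. Groups 1, 3 and 5 then divide first-line sunitinib cleanly. Documentation also moves to survival sheets after two Pfizer sequences, so requiring a third therapy fits the data collection poorly. This reading is plausible and may be what was intended. But the SAP does not state it, and it needs one phrase to mean one or more in the second position and zero or more in the third. A programmer following the text would exclude these patients, so the wording needs correcting on either view.

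Four stronger readings are tempting, and the documents do not support them.

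- A reader might infer that these patients are analysed nowhere else. SAP section 5 opens with "Analyses will be performed within each indication and treatment", so they are in the overall mRCC-axitinib results. Table 2.2-2 gives mRCC survival "5 by treatment sequence .6 by treatment and treatment line", Table 2.3-2 (.8, .9) gives PFS by line, and Table 1.1-1.2 counts sequences in all mRCC patients. The by-line tables do not isolate sunitinib-axitinib, however, and the SAP does not say whether its by-sequence tables use the seven groups.
- A reader might infer that temsirolimus-sunitinib patients without a third therapy are lost as well. They remain in group 4.
- A reader might take sunitinib-axitinib to be the registry's central population. The protocol presents the 92 as a historical comparison group for the Amendment VI question, which Amendment VII dropped.
- A reader might infer that PFS and quality of life are also flattered. The literal wording also drops patients still on axitinib without progression at data cut, which works the other way for PFS.

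**Conclusion.** The gap is real in the text of SAP section 5 and confined to the tables repeated for the seven groups. As written, patients who receive sunitinib then axitinib and nothing after are in no group, and neither are patients with another first-line drug followed by axitinib alone. Overall survival reported for the sunitinib-axitinib group would be too long, because membership requires surviving to a later therapy.

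The documents do not allow the size to be fixed. The illustrations give about 1.5 to 7.5 months in the median, with roughly 28 to 64 of 92 patients retained. They rest on assumed survival, exponential times and an assumed share starting a third therapy, and they run from the start of axitinib, whereas the baseline visit used for the sequence groups may be that of the first drug. No direction is claimed for PFS or quality of life. Because the evaluation is descriptive, this should be corrected before the final analysis but invalidates no test or decision rule.

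**What to change.** In SAP section 5, reword groups 1, 2 and 7 so that they apply with or without further therapy after the second drug. Add a descriptive row giving the share of each group that started a third therapy. State that the by-sequence tables 2.2-2 .5 and 2.3-2 .5 use the same definition. Use Table 1.1-1.2 to check that every first-line sunitinib or temsirolimus patient and every second-line axitinib patient falls in at least one group.

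The cost is a few lines of SAP text, a changed group flag and a rerun of the affected tables. No new data are needed.

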5.1 EFFECTIVENESS ANALYSIS SET

The effectiveness analysis set consists of all patients included into the study with at least one information on any of the following criteria: date of death, date of progression, assessment of response to therapy by the treating physician or an assessment to either effectiveness or tolerability of the therapy by the treating physician. For reporting the full analysis set will be labeled EAS.

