7.2. Study Setting

Inclusion and exclusion criteria:

- a) Patients with a histologically confirmed diagnosis of advanced renal cell carcinoma without prior therapy and at least 3 of 6 prognostic risk factors or relapsed/refractory mantle cell lymphoma for whom a decision was already made to treat with temsirolimus.
- b) Patients with histologically confirmed diagnosis of advanced/metastatic renal cell carcinoma or unresectable and/or metastatic GIST, after imatinib failure, for whom a decision was already made to treat with sunitinib.
- c) Patients with histologically confirmed diagnosis of advanced renal cell carcinoma after failure of prior therapy with sunitinib or a cytokine for whom a decision was already made to treat with axitinib.
- d) Written informed consent form from the patient is obtained prior to enrollment into the registry.

Due to the non-interventional nature of the registry, no specific requirements apply regarding the management of treatment. Dosing and duration of treatment will be decided by the physician according to individual treatment requirements of the patient.

Extract from the Summary of Product Characteristics

During the treatment of patients with temsirolimus, sunitinib, and axitinib, among other things, the section "Contraindications" of the respective Summary of Product Characteristics must be taken into account. In case of hypersensitivity reactions, the advice in the relevant Summary of Product Characteristics must be observed.

[figure not shown]
- a) In particular, the following excerpts are included under Section 4 "Clinical particulars" of the Summary of Product Characteristics of temsirolimus:
 - Hypersensitivity to the active substance or to any of the excipients of temsirolimus
 - It is recommended that patients be given an H1 antihistamine before an infusion of temsirolimus. In case of known hypersensitivity to antihistamines or in patients who cannot receive an antihistamine for another medical reason, temsirolimus should be used with caution.
 - Concomitant use of substances that affect CYP3A metabolism: CYP3A4 inducers: e.g. dexamethasone, carbamazepine, phenytoin, phenobarbital, rifabutin, rifampicin, St John's wort
 - CYP3A4 inhibitory agents: e.g. atazanavir, clarithromycin, indinavir, itraconazole, ketoconazole, nefazodone, nelfinavir, ritonavir, saquinavir, telithromyzine.
 - Concomitant use of sunitinib
 - Vaccinations
 - Pregnancy.

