The biometric evaluation of the patient data (including statistical analysis plan) takes place, appropriate to the design of a registry, in a purely descriptive manner, and will be performed by a Contract Research Organization (Winicker Norimed GmbH, Nuremberg). An annual interim analysis will be performed.

Definition of analysis set

All prospectively documented patients with a histologically confirmed diagnosis of renal cell carcinoma, MCL, and GIST will be included in the "safety population".

All patients to whom at least one of the following criteria apply will be included in the "efficacy population": Date of death, time of progression, physician's assessment of therapy response, or therapy assessment of efficacy and tolerability by the physician are available.

Retrospectively documented information will not be included in the analysis.

Analysis of Safety Criteria

The absolute and relative frequency of patients with adverse events will be shown in a tabular form, both globally and according to the system organ classes and the MedDRA "preferred terms". In addition, the absolute and relative frequency of therapy dropouts will be presented both overall and according to discontinuation reasons. Serious adverse events will be evaluated separately. Previous and concomitant therapies will also be tabulated.

Laboratory analysis and electrocardiogram results will be analyzed per visit. In addition, the physician will assess information on tolerability during therapy.

Analysis of Efficacy Criteria

The change in disease activity will be described using the following parameters:

[figure not shown]
- Assessment of response to therapy by the physician
- Physician's assessment of efficacy
- Overall survival (OS)
- Progression-free survival (PFS)
- Maximum Response

For the analysis in STAR-TOR, the duration of treatment is defined as the period between inclusion in the registry and occurrence of any of the events of either death or discontinuation of the documentation or termination of therapy.

The duration of treatment will be evaluated using methods from the field of "survival time analysis".

Other analysis parameters

Comorbidities will be coded in accordance with MedDRA and concomitant medications according to WHO-DD. Frequencies for appropriate coding levels will be presented. Evaluation of sequence and therapy regimens and quality of life (advanced RCC) will be performed.

Case number estimate

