5.2 SAFETY ANALYSIS SET

The safety analysis set consists of all prospectively documented patients included in the study with a histologically proven diagnosis of either renal cell carcinoma, MCL or GIST and at least one documented administration of temsirolimus, sunitinib or axitinib or any non-Pfizer treatment.

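### The SAP effectiveness set has no dose condition, so an enrolled but never-dosed patient can enter a drug's OS and PFS, realistically only through a death or progression date

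*SAP*

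**What the plan says.** SAP 5.1 admits patients to the EAS as follows: "The effectiveness analysis set consists of all patients included into the study with at least one information on any of the following criteria". The criteria are a date of death, a date of progression, a response assessment, or a physician's assessment of effectiveness or tolerability.

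SAP 5.2 restricts the safety set to "all prospectively documented patients included in the study with a histologically proven diagnosis of either renal cell carcinoma, MCL or GIST" who also have "at least one documented administration of temsirolimus, sunitinib or axitinib or any non-Pfizer treatment".

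Protocol section 11 (Definition of analysis set) uses nearly the same outcome rule for effectiveness: "All patients to whom at least one of the following criteria apply will be included in the" efficacy population. Its safety wording is "All prospectively documented patients with a histologically confirmed diagnosis of renal cell carcinoma, MCL, and GIST will be included in the" safety population, with no dose condition. After both definitions it adds: "Retrospectively documented information will not be included in the analysis".

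Protocol 7.2 enrols patients with confirmed histology, on the temsirolimus criterion those "for whom a decision was already made to treat with temsirolimus"; the sunitinib and axitinib criteria are built the same way. SAP 2.1 also makes the physician's decision to treat the condition for inclusion, and has eligibility checked at the baseline visit.

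SAP 8.2.3 assigns OS, PFS, response, FKSI-15 and EQ-5D to the EAS. SAP section 9 repeats tables for each combination of treatment and indication unless otherwise specified.

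**The concern.** The two SAP sets are built on different footings, and neither contains the other. The safety set asks whether the patient received treatment; the EAS asks only whether certain data exist. Since a patient can be enrolled before any dose is given, someone who never starts the drug can still contribute to the curves reported under it.

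The route in depends on outcome. An undosed patient has no response to therapy, effectiveness or tolerability to rate, and the flow charts place those ratings at follow-up or completion visits. That leaves a death or progression date as the realistic way in. Undosed patients with an event are admitted and those without are not. This is not an intention-to-treat principle, which would keep both, and it is not a treated-patient set, which would keep neither.

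At stake is the meaning of each drug's headline OS and PFS: some events could belong to people who never received the drug.

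**Working it through.** **Step 1. The definitions side by side.**

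| Condition | Protocol efficacy population | SAP EAS | Protocol safety population | SAP safety set |
|---|---|---|---|---|
| Outcome or rating available | required | required | no | no |
| Prospective documentation | general bar applies | not restated; protocol bar applies | required | required |
| Confirmed histology | entry criterion only | entry criterion only | required | required |
| At least one dose | no | no | no | required; non-Pfizer treatment also counts |

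The SAP added a dose condition to one set and not the other. That is the asymmetry at issue.

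**Step 2. Three patients traced through the rules.**

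- Enrolled, never dosed, dies: in the EAS, not in the safety set.
- Enrolled, never dosed, no death, progression or rating on record: in neither set.
- Enrolled, dosed, no outcome or rating on record: in the safety set, not in the EAS.

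So neither set contains the other. Table 1.1-6.1, which gives exclusion reasons relative to the most comprehensive set, has no clear reference set.

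**Step 3. Can OS and PFS be computed without a dose?** Yes. In SAP Appendix A1.3 both run from the baseline visit and use no dosing date; treatment duration, by contrast, runs from the first infusion. For PFS there is a further rule: if a death is recorded in survival follow-up and no progression was recorded earlier, progression is dated to the last visit plus 1 day. If an undosed patient's only visit was baseline, PFS = 1 + 1 = 2 days, or 2/365.25 × 12 = 0.07 months, whenever the death occurred.

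**Step 4. Size.** The plan states no figure that this point changes, and gives no share of undosed patients. What follows is illustration under assumed exponential survival.

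*Limiting case:* a share q of undosed patients has the event almost at once and the rest have median m. Solving (1 − q)·2^(−t/m) = 0.5 gives t = m·ln(2(1 − q))/ln 2.

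| Treated median (months) | q = 2% | q = 5% | q = 10% |
|---|---|---|---|
| 8 | 7.77 | 7.41 | 6.78 |
| 12 | 11.65 | 11.11 | 10.18 |

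*Milder case:* the undosed share f has its own median u of 1 to 3 months. Solving (1 − f)·2^(−t/m) + f·2^(−t/u) = 0.5:

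| Treated median (months) | f = 1% | f = 5% | f = 10% |
|---|---|---|---|
| 6 | 5.92–5.96 | 5.57–5.79 | 5.14–5.58 |
| 10 | 9.86–9.88 | 9.26–9.42 | 8.49–8.86 |

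At 1% the shift is at most 0.14 months; at 5% in the milder case it is 0.21 to 0.74 months.

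**The case against.** **The protocol has the same gap.** SAP 5.1 largely carries over the protocol's efficacy population, which also lacks histology and dose wording. A reader might infer that the SAP removed conditions the protocol had set for effectiveness; it did not. This stands, but it does not answer why a dose is required for one SAP set and not the other.

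**Retrospective and unconfirmed patients.** From the silence of SAP 5.1 a reader might infer that such patients enter OS and PFS. The documents do not support that. The protocol keeps retrospective information out of the whole analysis, in a sentence that follows both population definitions, and section 11 (Documentation during the treatment course) bars its collection. Histology is an entry criterion checked at baseline, so an unconfirmed patient would be an entry violation. What remains is narrow: SAP 5.2 states these filters and 5.1 does not, so anyone programming from 5.1 alone has no instruction to apply them.

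**Undosed patients are eligible.** True: enrolment needs only a decision to treat, so they do not breach the registry's criteria. Keeping everyone enrolled on that basis is defensible in a descriptive registry. But the EAS does not keep everyone; it keeps those with an event.

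**The scenario is narrow.** Protocol 10.2 allows for patients already on the drug at consent, for whom it cannot arise, and for patients who consent but are never enrolled. SAP section 5 also analyses within each indication and treatment, without saying how an undosed patient is assigned. These points limit the number affected; they do not close the route.

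**A dose condition can itself bias.** With the clock starting at the baseline visit, requiring a later dose guarantees survival up to that dose. This objection stands, and the fix has to deal with it.

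**Conclusion.** The point holds for never-dosed patients. SAP 5.1 lets them into a drug's OS and PFS by a route that in practice depends on having died or progressed. The documents do not show that any such patient exists, so the actual bias is unknown and may be negligible.

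The downward direction rests on undosed patients having their events earlier than treated ones. For PFS the last-visit-plus-1-day rule reinforces this; for OS, a late death in an undosed patient would not lower the estimate. The illustrated sizes also assume exponential survival and invented shares, and the limiting case is an upper end.

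The plan has no hypotheses or decision rules, so no formal conclusion turns on this. It affects how the descriptive curves are read, and it is cheap enough to correct that it should be corrected.

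**What to change.** 1. In SAP 5.1, define the EAS as patients in the safety analysis set who meet the existing data-availability condition. This brings in prospective documentation, confirmed histology and a documented dose together.
2. For each drug's tables, require a documented administration of that drug. Membership of the safety set is not enough, because SAP 5.2 also accepts any non-Pfizer treatment.
3. In Appendix A1.3, for patients first dosed after the baseline visit, start OS and PFS at the first documented dose, or present this as a sensitivity analysis, so that the dose condition does not create immortal time.
4. In Table 1.1-6.1, count the patients excluded as never dosed, not histologically confirmed, or retrospectively documented.

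If the sponsor prefers to keep undosed patients, the SAP should justify this and report their number per drug.

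The cost is a sentence in 5.1, a time-origin rule in the appendix, and a little programming. The EAS becomes slightly smaller, and the SAP departs from the protocol's efficacy-population wording; that departure must be noted.
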